#### STUDY DESIGN

Methodology: The design will be a RCT at a single site academic NICU-UVA Hospital in Charlottesville Virginia. Randomization will be stratified by birth weight (< 1000 grams and 1000-1500 grams) using a randomly permuted block design with random block sizes of 2 and 4. The intervention group will receive a novel multisensory, multimodal rehabilitative program, which will incorporate elements from the FNI program (scent exchange, touch, vocal soothing) as well as infant massage and parent-administered physical therapy. The intervention will be adjusted to take into account the infant's developmental stage and physiologic stability (See **Table 1**). Additionally, the intervention focuses heavily on interventions the parent can provide.

[figure not shown]

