#### Inclusion and exclusion criteria:

Infants will be eligible for this study if they meet the following criteria:

- GA at birth: ≤32 weeks gestation and/or birthweight ≤1500 grams
- Infants 7 days or older
- Parental ability to perform the interventions or identified designated surrogate (e.g. grandparent)
- Abnormal writhing GMs defined by the presence of a poor repertoire pattern on 2 consecutive weeks or the presence of a cramped-synchronized pattern on any assessment (see **Figure 1**)

Infants will be excluded from the study if they are clinically unstable (requiring high frequency mechanical ventilation, vasopressor support, need for continuous intravenous pain or sedation medication), if their parents do not speak English or if parental participation is hindered (e.g. incarceration or work/personal related issues).

Figure 1: Intervention algorithm

Intervention (n=30): Parents will be provided oral as well as written (Flip book) and illustrated information about the interventions. Study team members will assist with demonstrating appropriate technique for applying interventions and will use the teach-back method to ensure comprehension and understanding. Interventions will be developmentally tailored to the infant's GA (Table 1) as follows:

1. Modified FNI portion of the bundle includes:

[figure not shown]
- a. Vocal soothing: mothers will be instructed to express their feelings to their infant in their native language using varying intonations
- b. Scent exchange: on initial visit, mothers will receive 2 cloths, 1 to place in her bra and 1 to place under her infant's head. Cloths are subsequently exchanged at each visit.
- c. Comforting touch: mothers will be instructed to use gentle but firm and sustained touch by placing the infant's arms on the chest and placing their hand on top. The other hand will be used to gently contain the infants' feet, lightly drawing the knees towards the chest.
- d. Mother-Kangaroo-Care plus: kangaroo care will be combined with gentle touch, vocal soothing and eye contact as described above.
- 2- Infant massage: mothers will be taught moderate pressure massage by PT
- 3- Parent-administered PT: 10 minutes interventions promoting postural and head control as well as midline orientation will be conducted by the mother is recommended starting at 33 weeks' PMA. The intervention will be monitored by a physical therapist for 3 consecutive sessions and weekly thereafter.

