Qualitative analysis will included semi-structured interviews with adult participants as well as direct observations using qualitative description. Qualitative descriptive analysis will provide a comprehensive evaluation of the NICU multimodal rehabilitation program. The textual data from the interviews and observation notes will be analyzed by (1) immersion in the data (2) followed by line by line analysis and data reduction of the textual data through inductive open coding and constant comparative analysis. Tentative categories will be listed with each line of data and identified by "nodes" in the Dedoose software. (3) After line-by-line analysis of the transcripts, categories ("nodes") will be grouped together to form tentative themes.

Repeated measures models will be used to compare HINE and TIMP total scores at the time of discharge and at 3 months PMA between newborns in the standard care group and in the intervention group (NEO rehab program). F-tests based on contrasts will be used to make comparisons at the two specific time points. To approximate the power of the F-test for comparing the groups with respect to the 3-month HINE scores, the results in Romeo et al.(2008) were used. Their study showed that across CP diagnoses, the average 3 –month HINE score was approximately 40 with an estimated standard deviation of 8.8. A score of below 40 is associated with the GMFCS IV and V levels while a score of 40-60 is associated GMFCS levels I and II at 3 months of age. A score ≥ 73 is optimal. With 30 subjects per group, the two-sample t-test has 80% power, with a 2-sided significance level of 5% when the effect of the intervention is to increase HINE scores by 6.5 points. Allowing for 10% dropout, 33 patients per group are required. Similar analyses will be used for the TIMP scores as well as subscales of the HINE. For the GMA assessments, we will tabulate the proportion of children in each group classified as having poor repertoire, cramped/synchronized or chaotic movement abnormalities at each of the followup times. Markov models will be used to assess how the intervention affects the proportions of children transitioning between classifications. For all of the endpoints; this study will provide estimates of variation useful for planning a larger study of the rehabilitation program. Our primary analysis will be done as intention-to-treat.

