### **Ethics**

HSR IRB approval (#21502) was obtained prior to initiating any study procedures.

This proposed research will in human subject research. Institutional Review Board will be obtained. Informed consent will be obtained (supplemental attachment).

This proposal seeks to investigate the acceptability, feasibility, fidelity of a neonatal intensive care unit (NICU) rehabilitation program that will consist of gestational appropriate interventions. Additionally, we will determine the effects of short term motor outcomes of the program in premature infants identified to be at risk for cerebral palsy (CP). Will seek to enroll 60 participants.

Recruitment and Retention Strategies: Our study team has existing relationships with the academic NICU. The PI is a member of the Neuro NICU team. Study participants will have the opportunity to learn about the research and ask questions and make suggestions. The study participants will be meeting with a member of the research team weekly. Recruitment and retention rates will be monitors and considered an outcome measure to determine acceptability of the program.

Recruitment and Informed Consent

Participants will be recruited after IRB approval at the University of Virginia has been obtained. Patients will be recruited from the NICU after meeting the outlined inclusion/exclusion criteria. Informed consent will be obtained for all participants. There will be opportunities to ask questions, and are informed that they may withdraw from any part of the study at any time. Randomization will not occur until consent is obtained.

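### Randomisation is stratified by birth weight, but the HINE and TIMP models name no stratum term; if birth weight is prognostic, their standard errors are too large and the tests conservative

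*Combined protocol and SAP*

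**What the plan says.** The study design section of the combined protocol and SAP states: "Randomization will be stratified by birth weight (< 1000 grams and 1000-1500 grams"). Allocation within strata is made "using a randomly permuted block design with random block sizes of 2 and 4".

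The data management and statistical analysis section then says: "Repeated measures models will be used to compare HINE and TIMP total scores at the time of discharge and at 3 months PMA" between the standard care and intervention groups, with F-tests on contrasts at each of the two times. It names no covariate and excludes none. The supporting power statement is for an unadjusted comparison: "With 30 subjects per group, the two-sample t-test has 80% power" at a two-sided 5% level for a 6.5-point increase in HINE, using an SD of 8.8. The same section says that the study should supply variance estimates for planning a larger trial.

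The strata stop at 1500 g, whereas the inclusion criteria admit infants with "≤32 weeks gestation and/or birthweight ≤1500 grams". An infant of 32 weeks or less who weighs more than 1500 g is therefore eligible, but no stratum is stated for that infant.

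**The concern.** Stratified blocking makes the two arms nearly equal in birth-weight mix. If birth weight is related to the score, the difference between arms varies less from one randomisation to the next than it would under simple randomisation. A model without the stratum does not take this into account. It leaves the between-stratum variation in the residual, so it reports a standard error suited to a less balanced design. Confidence intervals come out too wide, the test rejects less often than 5% under the null, and some power is lost.

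Also at stake is what the pilot hands on. A model without the stratum yields only a total variance. A larger trial that stratifies and adjusts would also need the residual variance within strata.

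**Working it through.** **Inputs.** From the data management and statistical analysis section: 30 per group, difference 6.5, SD 8.8, two-sided 5%. From the study design section: two birth-weight strata, with random blocks of 2 and 4. Assumed, because the documents do not give them: R² from 0 to 30%, equal strata, the same stratum effect in both arms, and normal errors. Steps 1 to 4 treat the 3-month visit alone. The documents give no SD or effect for TIMP, so the figures are for HINE only.

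**1. The plan's own figure.** SE = 8.8 × √(2/30) = 2.272. Noncentrality = 6.5/2.272 = 2.861. The noncentral t with 58 degrees of freedom gives power 0.803, so the stated 80% reproduces.

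**2. Effect of leaving out the stratum.** Under balanced strata the true SE is about 2.272 × √(1−R²), while the unadjusted model still reports about 2.272.

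- Ratio 1/√(1−R²) at R² 5, 10 and 20%: 1.026, 1.054, 1.118.
- True level 2[1−Φ(1.96/√(1−R²))]: 4.4, 3.9, 2.8%.
- At R² 20% the true SE is 2.272 × √0.80 = 2.032. Unadjusted power is about Φ((6.5 − 2.002 × 2.272)/2.032) = Φ(0.96) = 0.83. Adjusted noncentrality is 6.5/2.032 = 3.20, which with 57 degrees of freedom gives power 0.882.

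**3. Simulation under the planned blocks.** 60 infants and 40,000 runs per row. Simulation standard errors are √(0.05 × 0.95/40,000) = 0.1 point for the level and √(0.8 × 0.2/40,000) = 0.2 point for power. Differences are taken before rounding.

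| R² | Type I, no stratum | Type I, with stratum | Power, no stratum | Power, with stratum | Power given up (points) |
|---|---|---|---|---|---|
| 0% | 5.0% | 4.9% | 80.3% | 80.3% | 0 |
| 5% | 4.5% | 5.0% | 80.8% | 82.1% | 1.3 |
| 10% | 4.0% | 5.0% | 81.5% | 84.3% | 2.8 |
| 20% | 2.8% | 4.8% | 82.8% | 88.2% | 5.4 |
| 30% | 1.9% | 4.9% | 84.1% | 91.9% | 7.8 |

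A separate simulation at R² 20% shows where the loss arises. The estimates themselves vary equally (SD 2.03 with or without the stratum), but the mean reported SE is 2.27 without the stratum and 2.03 with it.

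**4. What these R² values mean.** With equal strata, the gap between stratum means is 2 × 8.8 × √R². At R² 5, 10, 20 and 30% this is 3.9, 5.6, 7.9 and 9.6 HINE points.

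**5. Sensitivity.**

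- A 35/65 split of strata gives up 1.5, 2.6 and 5.6 points at R² 5, 10 and 20%.
- With 66 enrolled and 10% random dropout, the loss is 1.5, 2.7 and 5.9 points.
- In a two-visit model (within-infant correlation 0.5, stratum R² 0 at discharge and 20% at 3 months), power at 3 months is 82.7% without the stratum, 87.2% with a main effect only and 88.1% with a stratum-by-time term. Type I error is 3.0, 4.7 and 5.0%. The time term therefore matters when the stratum effect differs between visits.

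**6. Cost if the stratum explains nothing.** Error degrees of freedom per visit fall from 58 to 57, or to 56 with a third stratum. By noncentral t, power moves from 80.32% to 80.30% or 80.27%.

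**The case against.** The strongest reply is that nothing is wrong. The analysis text is brief and silent on covariates, which is not a decision against them, and the t-test is offered only to approximate the power of the F-test. The outcomes are secondary in a feasibility pilot, and no stated conclusion turns on them. The documents do not say that birth weight predicts HINE or TIMP. The larger R² values are also demanding: 20% needs a 7.9-point gap between strata, more than the 6.5-point treatment effect, from a single cut at 1000 g among infants already selected for abnormal general movements. At R² of 5% or less the loss is at most about 1.3 points. All of this stands, and it limits how much weight the point can carry. It does not remove the mismatch between design and model, which costs almost nothing to correct.

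A reader might infer more than the documents support:

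- **Bias or extra false positives.** Neither follows. The contrast is unbiased and the error is on the conservative side.
- **An underpowered comparison.** With 60 infants analysed, unadjusted power stays at or above 80%. A shortfall caused by dropout would be a matter of attrition, not of covariates.
- **A less precise estimate.** Blocking already secures the precision. What is overstated is the reported SE.
- **A need to adjust for entry movement pattern as well.** Each infant qualifies by a "poor repertoire pattern on 2 consecutive weeks or the presence of a cramped-synchronized pattern on any assessment". Since "Patients will be recruited from the NICU after meeting the outlined inclusion/exclusion criteria" and "Randomization will not occur until consent is obtained", this pattern is a legitimate baseline covariate. It is not a stratification factor, however, so leaving it out does not disturb the test's level. If uninformative, it costs about 0.6 point of power (30% cramped-synchronized assumed). Including it is a choice, not a requirement.

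**Conclusion.** The point holds as a modest improvement. The design stratifies by birth weight, and the HINE and TIMP models as written carry no stratum term. If birth weight is prognostic, the reported SE is too large by about 2.6, 5.4 and 11.8% at R² 5, 10 and 20%. The 5% test then runs at about 4.5, 4.0 and 2.8%, and about 1.3, 2.8 and 5.4 points of power are given up. If birth weight is not prognostic, the two analyses are equivalent.

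The direction follows from the design. The size rests on assumed R² values and on the plan's 3-month HINE inputs, with equal strata and dropout unrelated to stratum or arm. For TIMP and for the discharge visit only the direction can be stated. If the sponsor already intends to include the stratum, only the wording is missing.

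**What to change.** In the data management and statistical analysis section, add the birth-weight randomisation stratum and a stratum-by-time term as fixed effects in the HINE and TIMP repeated-measures models, coded as randomised. State in the study design section which stratum infants over 1500 g are assigned to, and use the same coding in the model. This is a separate gap in the randomisation description, but the model term cannot be defined until it is closed. Report the unadjusted contrasts alongside, and give both total and residual variance for planning the larger trial.

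The cost is one or two sentences of analysis text and one line on the strata, with no new data. The model gains two mean parameters (four with a third stratum). That is one or two error degrees of freedom per visit, which is less than 0.1 point of power. Entry movement pattern may be added as a further covariate if the sponsor wishes, provided it is named in advance.

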#### Innovation:

The possibility of intervention in the NICU is attractive because the brain is highly plastic and actively developing. Interventions at this stage may have a profound disease modifying impact.  Several investigators have evaluated the impact of early intervention strategies on neurodevelopmental outcomes in preterm infants reporting a positive effect on behavioral problems, social-relatedness, and cognitive and language performance. 

Infant massage represents a form of environmental enrichment that has a positive impact on multiple important outcomes after preterm birth including: improved weight gain, decreased stress and improved neurodevelopmental outcomes. Infant massage can be administered by NICU therapist (UVA has several therapists trained in infant massage) and the feasibility of infant massage by the mother is being actively investigated.

Similarly, early PT in the NICU leads to multiple positive outcomes including: increased bone mineralization and reduced incidence of motor delays in very low birth weight infants. Parent-administered PT has recently been shown to be feasible. Results from a recent RCT indicate that a 10 minute intervention twice a day for 3 weeks, from 34 to 36 weeks' PMA resulted in improved motor performance at 37 weeks' PMA. The intervention was supervised by a PT and was primarily designed to promote postural control, head control, and midline orientation.

Finally, studies have shown that interventions promoting the establishment of emotional connection between infant and mother, such as the Family Nurture Intervention (FNI) strategy, can positively impact neurodevelopmental outcomes at 18 months. The FNI targets infants 26-34 weeks PMA and aims to reduce the effects that abnormal sensory inputs in the NICU have on the developing brain. The program aims to enhance the emotional connection between mothers and their premature infants. Nurture specialists met with mothers on average 6.4 hours per week over the course of the NICU stay and continued until discharge (35-38 weeks' PMA). Elements of the FNI include mother/infant calming sessions with scent cloth exchange, vocal soothing, eye contact, kangaroo care, and family-based support sessions. It can be implemented shortly after birth and incorporates multiple elements of routine NICU care, an important point for implementation

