The short-term impact of these combined interventions on motor function will be assessed using the HINE, theGMA and the TIMP. These instruments will be administered at time of discharge from the NICU and at 3 months PMA. These instruments used in combination are recommended to be administered to infants before 5 months PMA and provide the most predictive of risk for CP. Instruments will be administered by certified providers and/or therapists. Additionally, demographic characteristics of the sample will be collected using the medical record and include: gender, ethnicity, race, gestational age at birth, birth weight and head circumference, primary diagnosis, neurologic comorbidities, medication management of neurologic comorbidities and neonatal abstinence syndrome, NICU length of stay,

feeding method upon discharge, discharge head circumference, geographical region, and disposition (death or discharge home).

Table 3: Short term developmental outcomes

Instrument	Measurement	Age	Interval
HINE	26 items used to assess cranial nerve function, posture, quality and quantity of movements, muscle tone, and reflexes and reactions). Each item is scored individually 0-3 with a sum score of all individuals ranging from 0-78. Lower the score the poorer the motor function. The HINE allows for identification of early signs of CP and individual items have demonstrated predictive value of motor outcome. Sensitivity 90% for prediction of motor outcome.	2 and 24 months of age	At time of discharge and 3 months PMA
GMA	Writhing stage 1) normal 2) poor repertoire- monotonous and lack complexity 3) cramped-synchronized- appear rigid and are not smooth or fluent in character. 4) chaotic -characterized by abrupt, large amplitude movements involving all limbs. Fidgety stage 1) normal 2) abnormal fidgety movements-absent or abnormal (exaggerated). Cramped-synchronized followed by absent fidgety pattern, have a 98% sensitivity and specificity for prediction of CP	Writing movements birth-9 weeks Fidgety movements 9- 20 weeks	Every 2 weeks during hospitalization and 3 months PMA
TIMP	28 observed items of spontaneous movements and 31 elicited items that assess the child's motor responses scored 0-6. The lower the score the poorer the motor function. The test is sensitive to age-related changes in motor performance ( $r = 0$ .83).	32 weeks to 4 months post term	At time of discharge and 3 months PMA

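### The HINE is to be formally compared between arms at NICU discharge, although Table 3 gives its age range as 2 to 24 months and nothing in the plan reconciles the two

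*Combined protocol and SAP*

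**What the plan says.** The section Data management and statistical analysis sets out the comparison: "Repeated measures models will be used to compare HINE and TIMP total scores at the time of discharge and at 3 months PMA". It then specifies a formal test at each visit, discharge included: "F-tests based on contrasts will be used to make comparisons at the two specific time points". It widens the scope: "Similar analyses will be used for the TIMP scores as well as subscales of the HINE". No covariate and no age-referenced score is named. The power statement in the same section concerns only the 3-month HINE.

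The section Expected outcomes of the study fixes the visits: "These instruments will be administered at time of discharge from the NICU and at 3 months PMA". In Table 3 of that section, the age column of the HINE row reads "2 and 24 months of age", while the interval column of the same row lists discharge and 3 months. The TIMP row says of that instrument: "The test is sensitive to age-related changes in motor performance", with r = 0.83, and gives its range as 32 weeks to 4 months post term.

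The plan gives no discharge age for this trial. The only one in the document belongs to a cited earlier programme, described under Innovation, whose sessions "continued until discharge (35-38 weeks' PMA".

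**The concern.** The age column of Table 3 reads as a range of applicability. With discharge at 35 to 38 weeks' PMA, the TIMP and GMA rows cover the visits planned for them. Only the HINE row does not. The analysis section nevertheless applies a formal between-arm test to the discharge HINE.

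Three things are at stake. A difference at discharge, or its absence, could not readily be read as a motor effect if the instrument is being used below its stated age. On one reading of age, the comparison would combine infants for whom the instrument applies with infants for whom it does not. And the plan says that for all endpoints the study will supply estimates of variation for a larger trial; a discharge HINE SD obtained outside the stated range would be a weak input.

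**Working it through.** **1. The plan's own figure.** Inputs from the analysis section: difference 6.5, SD 8.8, 30 per arm, two-sided 5%. The standardised difference is 6.5/8.8 = 0.739. The exact two-sample t-test has power 80.3%, so the stated 80% reproduces. It refers to the 3-month HINE and does not depend on the discharge visit.

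**2. HINE range on corrected age.** Assumptions: term is 40 weeks; one month is 4.348 weeks, so 2 months is 8.70 weeks.
- Lower limit: 40 + 8.70 = 48.7 weeks' PMA.
- Discharge at 38 weeks is 48.7 − 38 = 10.7 weeks too early; at 35 weeks, 13.7 weeks; at 40 weeks, 8.7 weeks.
- Only an infant still in the NICU at about 48.7 weeks' PMA would be in range.

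**3. HINE range on chronological age.** An infant born at gestational age G reaches 2 months at PMA G + 8.70.

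| Born at (weeks) | Reaches 2 months at (weeks' PMA) |
|---|---|
| 26 | 34.7 |
| 28 | 36.7 |
| 30 | 38.7 |
| 32 | 40.7 |

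For discharge at PMA D, infants with G > D − 8.70 are below range. The value of D is an assumption throughout.
- D = 35: 35 − 8.70 = 26.3 weeks.
- D = 38: 38 − 8.70 = 29.3 weeks.
- D = 40: 40 − 8.70 = 31.3 weeks.

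Since eligibility includes births up to 32 weeks, and later births at 1500 g or less, the contrast mixes infants inside and outside the range at any of these discharge ages.

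**4. Tests affected.** Table 3 describes the HINE as "26 items used to assess cranial nerve function, posture, quality and quantity of movements, muscle tone, and reflexes and reactions". If the subscales are these five areas (the plan does not list them), the discharge HINE accounts for 1 total + 5 subscales = 6 tests. The full HINE and TIMP set is (1 + 5 + 1) × 2 visits = 14. This counts tests; it does not measure bias or lost power.

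**5. TIMP and age at discharge.** Assumptions: score linear in age, with r = 0.83 over a uniform span of 25 weeks (roughly the TIMP range in Table 3).
- Slope: 0.83/(25/√12) = 0.115 SD per week.
- Residual variance: 1 − 0.83² = 0.311.
- If discharge is uniform over 35 to 38 weeks, the SD of age is 3/√12 = 0.87 week.
- Share of discharge variance due to age: 0.115² × 0.87²/(0.115² × 0.87² + 0.311) = about 3%.
- Equivalent sample: 30 × (1 − 0.031) = 29.1 per arm.

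**6. Cost of two baseline covariates.** With 60 infants and 2 covariates explaining a share R² of outcome variance, the variance of the treatment contrast changes by a factor of about (1 − R²) × 57/55.
- R² = 0: 6.5 × √(57/55) = 6.62.
- R² = 10%: 6.5 × √(0.90 × 57/55) = 6.28.
- Break-even: 1 − 55/57 = 3.5%.

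The plan gives no figure for R².

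**The case against.** The best defence is that discharge is a deliberate time point. It is named in Aim 2 and marks the end of the intervention, the outcomes are secondary, and the section on anticipated problems says that motor outcomes need further study. On that view the remedy is to reconcile one table row, and dropping a test beforehand is a preference. This largely stands, so the fix makes removal of the formal test conditional on what the reconciled range covers.

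It is also fair that the chronological cut-offs are unstable. The 35 to 38 weeks come from another programme. This trial selects infants with abnormal general movements, and Table 1 has a column for 37 weeks and above. Later discharge moves the cut-off up. In the other direction, 112 − 83 = 29 of the 112 very low birth weight infants admitted yearly are born after 32 weeks, and such infants would be further below range. The proportion out of range therefore cannot be fixed from the document; the mismatch remains at every discharge age examined. The statement that the instruments in combination are recommended before 5 months sets only an upper limit and does not resolve it.

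For the TIMP, the objection succeeds in substance: the loss is about 3% on the only discharge range available, below the 3.5% break-even for the covariates, which are in any case not age at test. A reader might take r = 0.83 to mean that age dominates the discharge TIMP. Table 3 does not give that correlation for discharge ages, and over a narrow age span its influence is small.

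**Conclusion.** The inconsistency is real and reaches a planned formal test. On corrected age, essentially all discharge HINE scores fall below the stated range. On chronological age, infants born after about 26 to 29 weeks do so if discharge is at 35 to 38 weeks' PMA, or after about 31 weeks if at 40. These results rest on term at 40 weeks and on assumed discharge ages. The consequence is a discharge HINE contrast, and a planning SD, that would be hard to interpret; its numerical effect on the estimate cannot be derived from the document.

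Three stronger inferences are not supported. The document does not show that the discharge HINE is out of range for every infant, because it does not say that age is corrected. It does not show bias in the discharge TIMP comparison: randomisation protects it unless the programme changes discharge timing, which the plan nowhere predicts. And neither the primary feasibility outcomes nor the 80% power for the 3-month HINE is affected. The point deserves correction before analysis but does not threaten the pilot's main purpose.

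**What to change.** 1. **HINE.** Reconcile the age and interval columns of the HINE row in Table 3, and state whether age is corrected or chronological. Unless the reconciled range covers discharge, make the 3-month HINE the only formally tested HINE contrast, and report the discharge total and subscales descriptively with PMA at test. Cost: one table row and a few sentences; the discharge HINE loses its formal test.

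2. **Baseline covariates (separate from the range problem).** Include birth weight and gestational age at birth in the HINE and TIMP models. Birth weight is the stratification factor; use it as continuous, because the strata stop at 1500 g while the gestational-age criterion admits heavier infants. Both variables are already collected. Cost: 2 degrees of freedom. The detectable 3-month HINE difference goes from 6.5 to about 6.6 if they explain nothing, and to about 6.3 if they explain 10% of the variance.

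3. **TIMP (optional).** Record PMA at each test and report a sensitivity analysis adjusting for it, labelled as a post-randomisation adjustment. The expected gain is small.
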